1.3 STUDY RATIONALE

Nutropin was approved by the FDA in 1994 for the treatment of GHD. In the ensuing years, many technical advances have been made in large-scale manufacturing methods for recombinant DNA products.

To use the most advanced methodology and equipment to ensure a continued supply of Nutropin AQ, Genentech has updated its manufacturing process while continuing to use the same *Escherichia coli* GH production system. Chemical and biological characterization (including potency) has demonstrated comparability of drug substance produced by the original and updated manufacturing processes and, based on this, the new manufacturing process that is used to produce Nutropin AQ v1.1 has been approved by FDA.

This study, performed in children with GHD, will assess the immunogenicity profile of Nutropin AQ produced by the new manufacturing process.

2. OBJECTIVES

The primary objective for this study is to characterize the immunogenicity profile of Nutropin AQ v1.1 when administered as a daily SC injection for 12 months (per the USPI for Nutropin AQ).

The clinical impact of immunogenicity will also be assessed during the course of the study by evaluating patients for functional growth attenuation in association with the development of anti-GH antibodies.

Nutropin AQ (Somatropin [rDNA origin])—Genentech, Inc. 24/Protocol ML29543, Version 2

3. STUDY DESIGN

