6. STATISTICAL CONSIDERATIONS AND ANALYSIS PLAN

6.1 DETERMINATION OF SAMPLE SIZE

A target enrollment of 80 patients was chosen to allow for a projected 10–15% dropout rate and exclusion of growth data for an estimated 10% of patients who might enter puberty during the study period and leave sufficient patient numbers to compare to previous studies of immunogenicity. This target enrollment was based on enrollment in a previous study (L0368) which planned to enroll 60 patients for the assessment of growth rate and change in height SDS. An initial sample size was chosen to ensure that at least 50 patients would complete the study (L0368 FR 30SEP97; Sec 4.8.4).

This study is expected to yield a minimum of 50 evaluable patients. Given a sample size of 50, and an assumed 50% of patients developing anti-GH antibodies, the 95% confidence interval around this proportion will be (35.53%, 64.47%). This interval was calculated using Clopper-Pearson methodology. Fluctuations in the proportion of

Nutropin AQ (Somatropin [rDNA origin])—Genentech, Inc. 47/Protocol ML29543, Version 2

patients developing anti-GH antibodies and the increase of evaluable patients will result in more precise confidence intervals. The exact confidence intervals for the scenarios for sample size of 50 and 60 in combination with the proportion of patients who are anti-GH antibody positive of 50% and 20% are listed in Table 3.

Table 3	Clopper-Pearson 95% Confidence Intervals for the Proportion of
	Patients Who Are Anti-GH Antibody Positive Based on 50 and
	60 Patients

N	Proportion of Patients Who Are Anti-GH Antibody Positive	95% Confidence Interval (Lower Limit)	95% Confidence Interval (Upper Limit)
50	0.5	0.3553	0.6447
60	0.5	0.3681	0.6319
50	0.2	0.1003	0.3372
60	0.2	0.1078	0.3230

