2.3 DETERMINATION OF SAMPLE SIZE

A target enrollment of 80 patients was chosen to allow for a projected 10–15% dropout rate and exclusion of growth data for an estimated 10% of patients who might enter puberty during the study period and leave sufficient patient numbers to compare to previous studies of immunogenicity. This target enrollment was based on enrollment in a previous study (L0368) which planned to enroll 60 patients for the assessment of growth rate and change in height standard deviation score (SDS). An initial sample size was chosen to ensure that at least 50 patients would complete the study (L0368 FR 30SEP97; Sec 4.8.4).

This study is expected to yield a minimum of 50 evaluable patients. Given a sample size of 50, and an assumed 50% of patients developing anti-GH antibodies, the 95% confidence interval (CI) around this proportion will be (35.53%, 64.47%). This interval was calculated using Clopper-Pearson methodology. Fluctuations in the proportion of patients developing anti-GH antibodies and the increase of evaluable patients will result in more precise confidence intervals. The exact confidence intervals for the scenarios for sample size of 50 and 60 in combination with the proportion of patients who are anti-GH antibody positive of 50% and 20% are listed in Table 1.

Nutropin AQ (Somatropin [rDNA origin])—Genentech, Inc. 5/Statistical Analysis Plan ML29543

Table 1

N	Proportion of Patients Who Are Anti-GH Antibody Positive	95% Confidence Interval (Lower Limit)	95% Confidence Interval (Upper Limit)
50	0.5	0.3553	0.6447
60	0.5	0.3681	0.6319
50	0.2	0.1003	0.3372
60	0.2	0.1078	0.3230

Clopper-Pearson 95% Confidence Intervals for the Proportion of Patients Who Are Anti-GH Antibody Positive Based on 50 and 60 Patients

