4.4.1 Primary Outcomes Endpoint

The primary endpoint for this study is the proportion of patients who develop anti-GH antibodies (i.e., with positive anti-GH antibody screening assay result) after initiating treatment with Nutropin AQ v1.1.

Among all patients with at least one post-baseline screening assay result, the number and percentage of patients who have at least one positive anti-GH antibody screening assay result at any post-baseline visit will be presented. The Clopper-Pearson exact 95% Cls for the percentage will also be provided.

An anti-GH antibody screening assay result is considered positive if the titer is \geq 1.0 mg/L.

4.4.2 Secondary Outcomes Endpoints

The secondary endpoints for this study are as follows:

- Proportion of patients who exhibit growth attenuation is defined as
 - (1) initial growth response greater than pretreatment velocity followed by reduction in growth response to below the pretreatment velocity in the subsequent 6- to 12month treatment period

or

(2) reaching \leq 2 cm per year at any scheduled visit: Month 3, 6, 9, or 12

Please note that for criteria (1), the initial growth response occurs as early as Month 3 and growth attenuation status at post-baseline visit will be evaluated at Months 6, 9, or 12.

The growth response is based on the annualized growth velocity defined as (height - baseline height)/ (date of height assessment – date of baseline)*365.25 at any post-baseline visit.

Pretreatment growth velocity is defined as (Baseline height – last historical height) / (date of baseline – date of last historical height)*365.25

Growth attenuation status at post-baseline visit Tk (=Month 6, Month 9 or Month 12 for k=6, 9, or 12) will be classified as follows:

Yes: If growth velocity at Tk< pretreatment growth velocity and there is Tj < Tk with growth velocity at Tj > pre-treatment growth velocity, for j<k, and k=6, 9, or 12 or growth velocity \leq 2 cm per year at any scheduled visit: Month 3, 6, 9, or 12 **No:** Otherwise.

Nutropin AQ (Somatropin [rDNA origin])—Genentech, Inc. 9/Statistical Analysis Plan ML29543 • 2x2 cross tabulation (with frequencies and percentages) of growth attenuation status (yes or no) and anti-GH antibody status (positive or negative) will be provided for each antibody assay at each visit (Month 6, 9, and12).

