4.7 MISSING DATA

Missing data will not be imputed for efficacy outcome measures. All available assessments will be reported with associated number of observations. If a patient discontinues study medication before the end of the 1-year treatment period, their growth rate will be computed for the last 3-month interval visit and used in the calculation of mean growth for that time interval only.

Nutropin AQ (Somatropin [rDNA origin])—Genentech, Inc. 13/Statistical Analysis Plan ML29543

There are two criteria for defining growth attenuation: (1) initial growth response greater than pretreatment velocity followed by reduction in growth response to below the pretreatment velocity in the subsequent 6- to 12-month treatment period, or (2) reaching \leq 2 cm per year at any scheduled visit: Month 3, 6, 9, or 12.

For criteria (1), if the pretreatment velocity is missing then growth attenuation is missing. Otherwise,

- 1. If patient discontinued < month 3, the growth attenuation will be missing because the initial growth response cannot be determined for criteria (1).
- 2. If patient discontinued \geq month 3 and < month 6, then:
 - a. If the height on Month 3 is missing, the growth attenuation will be missing because the initial growth response cannot be determined.
 - b. If the height on Month 3 is non-missing, the initial growth response can be determined but the growth attenuation cannot be determined because there is no Month 6 visit to determine the reduction in growth response to below the pretreatment velocity.
- 3. If patient discontinued ≥ month 6, the growth attenuation will be calculated based on the original definition.

For safety analyses, incomplete onset dates for adverse events and concomitant medications will be imputed according to the following algorithm:

- If the day is missing, the 1st of the month will be used.
- If the day and month are missing, January 1st will be used.

In cases where the imputation of the start/onset date leads to adverse events or concomitant medications occurring before treatment start, the start date will be set to the treatment start date.

Incomplete end dates for non-ongoing adverse events or concomitant medications will be imputed according to the following algorithm:

- If the day is missing, the last day of the month will be used.
- If the day and month are missing, December 31st will be used.

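### Children who leave antibody-negative before Month 12 count as fully negative in the primary proportion, so it tends to understate 12-month incidence by an amount smaller than its interval half-width

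*SAP*

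**What the plan says.** The primary objective in Protocol section 2 is to "characterize the immunogenicity profile of Nutropin AQ v1.1 when administered as a daily SC injection for 12 months". Blood is drawn at Months 1, 3, 6, 9 and 12, or at early discontinuation (Protocol 4.3.2).

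SAP 4.4.1 sets the denominator as "Among all patients with at least one post-baseline screening assay result" and the numerator as those with "at least one positive anti-GH antibody screening assay result at any post-baseline visit will be presented", with a Clopper-Pearson 95% interval. It requires no minimum follow-up, and the endpoint sentence names no time point.

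Early departure is expected. According to Protocol 6.1, "A target enrollment of 80 patients was chosen to allow for a projected 10–15% dropout rate", with a further 10% losing growth data through puberty.

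For growth attenuation, SAP 4.7 treats criterion 1 as missing or undeterminable for children who leave before Month 6. For later leavers it says: "If patient discontinued ≥ month 6, the growth attenuation will be calculated based on the original definition". That definition (SAP 4.4.2) defaults to 'No' whenever the 'Yes' condition is not met.

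**The concern.** A child who leaves after a negative Month 1 sample contributes one month of observation and is scored like a child negative for a year. Within a fixed denominator, cutting follow-up short can lose positives but cannot create them. Relative to 12-month incidence, the error therefore runs one way: down.

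The direction matters because of how the result will be used. Protocol 3.3.3 says the data will help determine whether the updated product's immunogenicity differs from the original's, and Protocol 6.1 sizes the study for comparison with earlier immunogenicity studies. A percentage with no stated follow-up duration is hard to compare with another study's, and a downward error is on the reassuring side.

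**Working it through.** **1. The plan's own figures.** The SAP says of its example interval: "This interval was calculated using Clopper-Pearson methodology". Recomputing SAP Table 1 from beta quantiles gives 0.3553–0.6447 (25/50), 0.3681–0.6319 (30/60), 0.1003–0.3372 (10/50) and 0.1078–0.3233 (12/60). All agree except the last upper limit, printed as 0.3230, which is immaterial. At N=80 the same method gives 11.9–30.4% for 16/80 (half-width 9.3 points) and 38.6–61.4% for 40/80 (half-width 11.4 points).

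**2. Inputs.** From the documents: dropout d = 0.10 or 0.15, planning proportions p = 0.20 or 0.50, and the five sampling times. Assumed, because the documents do not give them: when antibodies first appear, when children leave, and that leaving is unrelated to antibody status.

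**3. Formula.** Let F be the fraction of 12-month seroconversions visible by a leaver's last sample. The expected crude proportion is p × [(1 − d) + d × mean F], so the shortfall is p × d × (1 − mean F).

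**4. Leavers spread evenly over last samples at Months 1, 3, 6 and 9.**
- Early onset (40, 30, 15, 10 and 5% of seroconversions at the five visits): mean F = (0.40 + 0.70 + 0.85 + 0.95)/4 = 0.725.
- Onset even in time: mean F = (1/12 + 3/12 + 6/12 + 9/12)/4 = 0.396.
- Late onset (one third each at Months 6, 9 and 12): mean F = (0 + 0 + 1/3 + 2/3)/4 = 0.25.

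| Shortfall, points | p=20%, d=10% | p=20%, d=15% | p=50%, d=10% | p=50%, d=15% |
|---|---|---|---|---|
| Early onset | 0.55 | 0.83 | 1.38 | 2.06 |
| Even onset | 1.21 | 1.81 | 3.02 | 4.53 |
| Late onset | 1.50 | 2.25 | 3.75 | 5.63 |

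**5. Leaving uniform over 12 months, with a sample at exit.** Even onset gives p × d / 2: 1.0–1.5 points at 20% and 2.5–3.75 at 50%. Onset even over the first six months and complete by Month 6 gives p × d / 4: 0.5–0.75 and 1.25–1.9 points.

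**6. Bound.** If no leaver's seroconversion is seen before exit, the shortfall is p × d. At d = 0.15 that is 3.0 points at 20% and 7.5 points at 50%.

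**7. Simulation** (80 children, 4,000 runs per scenario, leaving times as in step 4). Coverage of the true 12-month figure by the nominal 95% interval was 95–97% at 20% and 86–96% at 50%. It was lowest with late onset and 15% dropout, where the mean crude proportion was 44.3%, a shortfall of 5.7 points. Kaplan-Meier averaged 19.9–20.1% and 49.9–50.2%, so it recovers the target when dropout is unrelated to antibody status.

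**8. Attenuation.** Assume a true risk of 2–10%, events spread equally over Months 6, 9 and 12, and later leavers split equally between last visits at Months 6 and 9, so that half of their events are seen. With risk 10%, d = 0.15 and all leavers at or after Month 6, the shortfall is 0.10 × 0.15 × 0.5 = 0.75 points. With risk 2%, d = 0.10 and half of the leavers gone before Month 6 (set to missing), the proportion is 0.02 × (0.90 + 0.05 × 0.5)/0.95 = 1.95%, a shortfall of 0.05 points. If no late leaver's event is seen, the largest figure is 0.10 × 0.15 = 1.5 points.

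**The case against.** The strongest reply is that the endpoint, as written, is the proportion with any positive sample after treatment starts. It has no time point, and the analysis is descriptive with no hypothesis test. For that quantity the crude proportion and exact interval are legitimate. This stands: the shortfall is relative to the 12-month objective, not to the endpoint sentence, so the planned figure should not be displaced.

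The plan also limits the loss. Early leavers are asked for a final immunogenicity sample (Protocol 4.5.5), and children who only stop treatment may stay and be sampled (Protocol 4.6.2). SAP 4.2 tabulates participation duration and SAP 4.6.3 lists assay results by patient and visit, so short follow-up will be visible. These points reduce the problem but do not remove it, because no figure in the text available estimates 12-month incidence.

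Four stronger readings are tempting, and the documents do not support them:
- *Every early leaver is scored as a non-event.* A child positive, or already attenuated, before leaving counts as an event.
- *Puberty adds to the primary shortfall.* Protocol 3.1 keeps those children in the study and assesses their antibody data.
- *The attenuation proportion is necessarily biased low.* Criterion 1 is missing or undeterminable for leavers before Month 6, and leaving them out could move the proportion either way.
- *The SAP has no sensitivity analysis.* Its contents list a section 4.4.4, but the text between 4.4.3 and 4.5 was not available, so this cannot be said.

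Nor do the documents say that antibodies appear slowly. The 3–6 month pattern in Protocol 3.3.3 concerns growth in rare attenuation cases. If onset is early, the shortfall is small.

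**Conclusion.** The point holds for the primary endpoint in a limited form. The SAP 4.4.1 proportion mixes follow-up durations and tends to understate 12-month incidence, because children who leave negative stay in the denominator as fully negative. With 10–15% dropout the expected shortfall is roughly 0.5 to 2.3 points at a true 20% and 1.2 to 5.7 points at a true 50%. Both ranges lie below the N=80 half-widths of about 9 and 11 points. They rest on assumed onset and leaving times and on dropout unrelated to antibody status. A cheap supplementary analysis is worth adding; the planned primary analysis does not need replacing. For attenuation, the corresponding effect from children followed only part of the way from Month 6 to Month 12 is likely under 1 point.

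**What to change.** Keep the SAP 4.4.1 proportion and its exact interval as the planned primary figure. Add beside it, labelled supplementary, a Kaplan-Meier (life-table) cumulative incidence at 12 months with a 95% interval, over Months 1, 3, 6, 9 and 12. Censor each negative child at the last sample and show the number sampled at each visit. State that the estimate assumes dropout is unrelated to antibody status. The cost is a paragraph of SAP text and one table from data already collected; the downside is that assumption, which the data cannot verify.

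For attenuation, do not simply remove children who lack both a 'Yes' and a Month 12 height. That keeps a 'Yes' who later left and drops a 'No' who left, which selects on outcome. As an illustration with assumed values, take 80 children, a true risk of 10%, and 9 children with partial follow-up, half of whose 0.9 expected events are seen. The SAP rule gives (8 − 0.45)/80 = 9.4%. Dropping the 9 − 0.45 = 8.55 incomplete 'No' children gives 7.55/71.45 = 10.6%, an upward error of similar size. At most, apply the same censored life-table estimate, or report how many 'No' children lack a prepubertal Month 12 height, and note that the effect is likely under 1 point.

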3.3.3 Rationale for Antibody Assay Assessments

As with all therapeutic proteins, there is potential for immunogenicity. In the case of GH, antibodies with GH binding capacities below 2 mg/L have not been associated with growth attenuation (*refer to the USPI for Nutropin AQ*). In a very small number of patients treated with Nutropin AQ, where binding capacity was above 2 mg/L, interference with growth response was observed. In clinical studies of pediatric patients who were treated with Nutropin or Nutropin AQ for the first time, antibodies with binding capacities ≥ 2 mg/L were not observed in any patients at 6 months *or* 15 months for Nutropin AQ, respectively (refer to the USPI for Nutropin AQ).

In this study, all serum samples taken for immunogenicity assessments will be analyzed in an anti-GH antibody screening assay. Any samples positive for anti-GH antibody with a titer > 2.4 mg/L will *then* be analyzed in an anti-GH neutralizing antibody assay and an anti-GH antibody binding capacity assay. Neutralizing antibody assays are an additional method for assessing anti-therapeutic antibodies that can result in changes in the toxicology, pharmacokinetics, and efficacy of biotechnology-derived pharmaceuticals. Growth attenuation due to the development of neutralizing anti-GH antibodies is rare and, when reported, usually occurs in patients with mutations in the GH encoding gene (Schwarz et al. 1987; Cogan and Phillips 2006). When this rare event occurs, the growth response in the first 3–6 months is followed by a rapid decline in annualized

Nutropin AQ (Somatropin [rDNA origin])—Genentech, Inc. 26/Protocol ML29543, Version 2

Clinical Study Report: Nutropin AQ (Somatropin)—Genentech, Inc. 375/CSR ML29543

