6.3.1 Primary Endpoint

The primary endpoint for this study is the proportion of patients who develop anti-GH antibodies after *initiating* treatment with Nutropin AQ v1.1.

6.3.2 Secondary Endpoints

The secondary endpoints for this study are as follows:

- Proportion of patients who exhibit growth attenuation (defined as initial growth response greater than pretreatment velocity followed by reduction in growth response to below the pretreatment velocity in the subsequent 6- to 12-month treatment period or reaching ≤2 cm per year)
 - Cross tabulation between growth attenuation status (i.e., with or without) and anti-GH antibody status (i.e., positive or negative) will be provided for any

Nutropin AQ (Somatropin [rDNA origin])—Genentech, Inc.

48/Protocol ML29543, Version 2

antibody and for neutralizing anti-GH antibody, respectively, at each visit. Similar tables will also be provided for patients who had at least one positive anti-GH antibody (anti-GH antibody and neutralizing antibody, respectively) at any follow-up visit against those who never developed antibody after treatment.

- Proportion of patients with neutralizing antibody among those who had positive anti-GH antibody
 - This analysis will be summarized by visit, as well as *cumulatively*, for patients who had detectible anti-GH antibody at any post-baseline visit, as well as those who *remained negative throughout the study*.
- Annualized 6- and 12-month growth velocities and height SDS will be summarized separately for patients who were anti-GH antibody-positive at any post-baseline follow-up visit and those who were anti-GH antibody-negative at all visits (including baseline). Graphic displays of the individual patient growth patterns along with the longitudinal antibody profile over the course of the study will be prepared. Patients who enter puberty during the study period will be included up to the last visit at which they were determined to be prepubertal.

Additional analyses deemed appropriate for assessing immunogenicity will be described in the Statistical Analysis Plan.

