Similar tables of growth attenuation status (yes at any visit from Month 6 to Month 12) and anti-GH antibody status for those who had a positive antibody assay at any follow-up visit (negative at baseline) and those who remained negative throughout the study (including baseline) will also be provided.

- Proportion of patients with neutralizing anti-GH antibody (Nab positive) among those who had positive anti-GH antibody. This analysis will be summarized by visit, as well as cumulatively, for patients who had detectible anti-GH antibody (ATA) at any post baseline visit (with negative antibody assay at baseline), as well as those who remained negative throughout the study (including baseline).
- Annualized 6- to 12- month growth velocities and height SDS. These variables will be summarized separately for patients who were anti-GH antibody-positive at any post-baseline follow-up visit (negative at baseline) and those who were anti-GH antibody-negative at all visits (including baseline).

The difference between the annualized 6- and 12- month growth velocities will be presented separately for patients who were anti-GH antibody-positive at any post-baseline visit and those who were anti-GH antibody-negative at all visits (including baseline).

Graphic displays of the individual patient growth patterns (growth velocity); along with the longitudinal antibody profile over the course of the study will be prepared.

For the above analyses, if there is any patient who appears to have positive anti-GH antibody at baseline, they will be summarized separately from the other groups.

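### In the by-visit growth attenuation rule, the 2 cm/yr limb is not tied to visit Tk, so as written a Month 9 or 12 value can set the Month 6 or 9 status

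*SAP*

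**What the plan says.** SAP 4.4.2 opens the by-visit rule with "Growth attenuation status at post-baseline visit Tk (=Month 6, Month 9 or Month 12 for k=6, 9, or 12) will be classified as follows". A child is Yes at Tk by either of two limbs joined by *or*, and No otherwise.

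- **Limb (1)** needs a velocity at Tk below the pretreatment velocity, and that "there is Tj < Tk with growth velocity at Tj > pre-treatment growth velocity, for j<k, and k=6, 9, or 12".
- **Limb (2)** needs a velocity at or below "2 cm per year at any scheduled visit: Month 3, 6, 9, or 12". The join reads "growth velocity at Tj > pre-treatment growth velocity, for j<k, and k=6, 9, or 12 or growth velocity", and what follows does not mention Tk.

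Velocity is annualized and cumulative from baseline. The 2x2 tables of this status against antibody status "will be provided for each antibody assay at each visit (Month 6, 9, and12". A further set is described as "Similar tables of growth attenuation status (yes at any visit from Month 6 to Month 12".

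Nothing elsewhere supplies the missing index. The timing note in SAP 4.4.2 covers criterion (1) only. SAP 4.7 repeats the unindexed wording, and its steps for early discontinuation also address criterion (1) only. Protocol 6.3.2 describes the endpoint as a fall below the pretreatment rate "in the subsequent 6- to 12-month treatment period or reaching ≤2 cm per year" and asks for a cross-tabulation at each visit, but gives no visit-level rule for the 2 cm threshold.

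**The concern.** A status attached to a visit should use data available at that visit. Limb (2) as written takes one value per child and repeats it at Months 6, 9 and 12, so a first low value at Month 12 is also recorded at Months 6 and 9.

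Timing matters for this question. Protocol 3.3.3 describes antibody-related attenuation as a sequence: "the growth response in the first 3–6 months is followed by a rapid decline in annualized" velocity, to below pretreatment rates. The by-visit tables are where antibody status and growth status are paired at the same time. Take a child who is antibody-negative at Month 6, turns positive later and first reaches 2 cm/yr or less at Month 12. The literal rule enters that child in the Month 6 table as attenuated and antibody-negative, which is misleading about the order of events.

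The text also leaves programmers a choice between the literal rule, a rule at Tk and a rule up to Tk. These can give different tables.

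**Working it through.** No figure in the plan depends on this rule, so there is nothing to reproduce. The check applies the rule to height paths. The paths are assumptions for illustration; the formula and target days come from the SAP.

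**Inputs.** Velocity = height gain / days × 365.25 (SAP 4.4.2). Target Days are 90, 180, 270 and 360 (SAP Table 2), taken as elapsed days. Counting from Day 1 instead changes the second decimal and none of the statuses.

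**Step 1: one path in full.** Pretreatment 2.5 cm/yr; gains 0.9, 1.5, 1.9 and 1.95 cm.

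- Month 3: 0.9/90 × 365.25 = 3.65
- Month 6: 1.5/180 × 365.25 = 3.04
- Month 9: 1.9/270 × 365.25 = 2.57
- Month 12: 1.95/360 × 365.25 = 1.98

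At Months 6 and 9 the velocity is above 2.5, so limb (1) fails, and it is above 2. Only Month 12 qualifies on its own data. The literal limb (2) is met at all three visits by the Month 12 value.

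**Step 2: other paths.** Status is given at Months 6/9/12. In these five paths, indexing limb (2) at Tk and indexing it up to and including Tk give the same answer.

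| Pretreatment | Velocities at Months 3/6/9/12 | As written | Indexed |
|---|---|---|---|
| 2.5 | 3.65, 3.04, 2.57, 1.98 | Yes/Yes/Yes | No/No/Yes |
| 2.5 | 3.65, 2.64, 1.96, 1.93 | Yes/Yes/Yes | No/Yes/Yes |
| 3.5 | 4.06, 3.86, 2.64, 1.99 | Yes/Yes/Yes | No/Yes/Yes |
| 5.0 (no earlier response) | 4.50, 3.51, 2.50, 1.95 | Yes/Yes/Yes | No/No/Yes |
| 4.5 | 5.28, 3.86, 2.64, 1.99 | Yes/Yes/Yes | Yes/Yes/Yes |

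In the last row limb (1) is already met at Month 6 (3.86 < 4.5 after 5.28 > 4.5), so look-ahead adds nothing.

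**Step 3: which statuses can look ahead.** Limb (2) alone has 2 × 2 × 2 × 2 = 16 low/not-low patterns over four visits, hence 16 × 3 = 48 pattern-visits. The literal rule differs from the up-to-Tk rule in 4:

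- Month 6: no low value at Months 3 or 6, and one at Month 9, Month 12 or both (3 patterns).
- Month 9: low at Month 12 only (1 pattern).
- Month 12: none.

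Each of these patterns is also Yes at Month 9 or 12 on its own data, so any-visit status does not change.

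**Step 4: how far ahead the rule can reach.** Without height loss, an earlier gain cannot exceed the Month 12 gain. If Month 12 velocity is at most 2, velocity at an earlier visit is at most 2 × (Month 12 day)/(earlier day).

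| Visit timing | Cap at Month 6 | Cap at Month 9 |
|---|---|---|
| Target days | 2 × 360/180 = 4.0 | 2 × 360/270 = 2.67 |
| ±3 days (Protocol Appendix 1) | 2 × 363/177 = 4.10 | 2 × 363/267 = 2.72 |
| Extremes of the SAP Table 2 windows | 2 × 405/136 = 5.96 | 2 × 405/226 = 3.58 |

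Every cap exceeds 2, so a child can be above the threshold at Month 6 or 9 and still be classified by a later value.

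**The case against.** The strongest reply is that little is at stake. The study plans no hypothesis test (SAP 4), the endpoint is secondary, and listings and individual plots show when each value occurred. Look-ahead needs near-arrest of growth on treatment. Protocol 3.3.3 calls attenuation from neutralizing antibodies rare, and effects on growth very rare in children without a mutation. Exposure is reduced further because a fall below pretreatment velocity is a listed possible reason for withdrawal (Protocol 4.6.1), and growth data stop at the last prepubertal visit (SAP 4.4). All of this stands. It limits the size of the problem but does not supply the missing index.

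A second reply is that a programmer would naturally read limb (2) as applying at Tk. The words do not support that: Month 3 is listed, and Month 3 is not a Tk.

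A reader might also infer that carrying a low Month 3 value forward into the later tables is a fault. The documents do not support this. The protocol speaks of *reaching* the threshold, and SAP 4.4.2 and 4.7 name Month 3 explicitly, so a status that persists once reached is a fair reading. Only the look-ahead is a clear error.

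**Conclusion.** The by-visit rule is wrong as written, and the consequence is small. A first value of 2 cm/yr or less at Month 9 or 12 can set the status at an earlier visit. The effect is confined to the descriptive Month 6 and Month 9 tables. The number of children affected cannot be computed from the documents and may be zero.

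Three stronger readings should be avoided.

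- A reader might infer that the overall attenuation proportion or its association with antibodies over the whole study is distorted. Look-ahead changes neither the patient-level proportion, the any-visit status, the Month 12 status nor the primary endpoint.
- A reader might infer from the 4.0 cap that an early responder with a pretreatment velocity above 4.0 is always Yes at Month 6 by limb (1). That holds only at exact target days. With pretreatment 4.5 and gains of 1.3, 1.9, 2.0 and 2.1 cm at Days 90, 150, 270 and 390, all inside the SAP windows, the velocities are 5.28, 4.63, 2.71 and 1.97. Limb (1) is not met at Month 6, yet the literal status is Yes.
- A reader might express the effect as a percentage per child, such as 1/50 = 2.0 points. That measures table size, not likelihood. The antibody proportions in SAP 2.3 concern developing antibodies during the study, not positivity at a visit.

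The conclusion about the text needs no assumption. The worked statuses rest on the illustrative height paths, and the caps on no height loss and the stated visit days.

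**What to change.** In the Tk rule of SAP 4.4.2, change limb (2) to: *or growth velocity ≤2 cm per year at any scheduled visit up to and including Tk*. Label the Month 6, 9 and 12 tables as cumulative. This removes the look-ahead and keeps the SAP's stated counting of Month 3.

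If a visit-specific status is intended, write *at Tk* instead. Then keep the numbered definition (Month 3, 6, 9 or 12) as a separate patient-level variable, used for the overall proportion and the any-visit table. Otherwise children low only at Month 3 could drop out of that table.

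This alternative has a small downside: a child low only at Month 9 returns to No at Month 12 unless limb (1) is met. With pretreatment 1.5 and velocities 3.04, 2.54, 1.89 and 2.54, the status is No/Yes/No at Tk and No/Yes/Yes up to and including Tk. The patient-level variable still counts that child.

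The cost of the first option is one phrase, a table label and one line of programming. The alternative adds one derived variable. Neither needs new data.
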